5.5. Potential Benefits

Most subjects are expected to benefit from the desensitization and aspirin treatment following **Visit 2** of the study. There is a small potential benefit to individual subjects while taking ifetroban if it improves chronic symptoms or decrease the severity of response to aspirin challenge. If TP receptor antagonism does block features of the reaction to aspirin or improves symptomatic control of AERD, it would support the use of ifetroban or other TP receptor antagonists as potential therapeutic agents in AERD. Thus, the studies should shed light on how to improve therapy for AERD and better understand how these therapies work.

The risks associated with the treatments in this study are identifiable and small. There is extensive experience with ifetroban, and the brief period during which individuals are being treated with both ifetroban and aspirin are not likely to substantially increase the risk of bleeding. Furthermore, the risk of severe reactions to aspirin challenges are low, and such reactions can be readily managed in the study setting.

6. Investigational Agent /Device/Intervention

6.1. Investigational Agents/Devices/Interventions

6.1.1. Investigational Agent #1

Ifetroban: Cumberland Pharmaceuticals

6.1.1.1. Formulation, Packaging, and Labeling

Description of the Formulation: Ifetroban capsules are formulated as a dry powder blend and filled into hard gelatin capsules. The formulation consists of Ifetroban, mannitol, microcrystalline cellulose,

crospovidone, magnesium oxide, colloidal silicon dioxide, and magnesium stearate. Capsules are filled into high density polyethylene bottles and sealed with screw-cap closures.

Stability Characteristics of the Formulation: Ifetroban capsules are part of an ongoing stability study to support long term use in clinical studies. Available data suggest the capsules will be stable for at least 24 months.

6.1.1.2. Dosage, Preparation, and Administration

Oral Ifetroban is supplied as a 50mg capsule (4 capsules will be provided for each 200mg dose) for oral administration and is taken once daily. It is stored at controlled room temperature.

6.1.2. Investigational Agent #2

Placebo: Cumberland Pharmaceuticals

6.1.2.1. Formulation, Packaging, and Labeling

Description of the Formulation: Placebo for ifetroban capsules are formulated as a dry powder blend filled into capsules. The formulation consists of microcrystalline cellulose, crospovidone, colloidal silicon dioxide, and magnesium stearate. Capsules are filled into high density polyethylene bottles and sealed with screw-cap closures.

6.1.2.2. Dosage, Preparation, and Administration

Placebo capsules will be supplied for oral administration and 4 capsules will be taken once daily. It is stored at controlled room temperature.

6.1.3. Investigational Agent #3

Aspirin

6.1.3.1. Formulation, Packaging, and Labeling

- Active ingredient: Aspirin
- Doses will range from 40 mg- 650 mg.
- Doses will be given in the form of yellow (81 mg) or orange (325 mg) tablets.
- Store aspirin between 20° and 25° C (68° and 77° F).
- Manufactured by Rugby Laboratories, Duluth, Georgia.

6.1.3.2. Dosage, Preparation, and Administration

Aspirin will be open label. We will increase the dose of aspirin from 40 mg to 325 mg during the course of a day. All aspirin will be taken by mouth and should be taken with plenty of water. We will obtain the aspirin for this study from the IDS pharmacy. They will count and dispense the correct amount of aspirin needed. For the 40 mg dose of aspirin, we will use ½ of a chewable 81 mg tablet of aspirin.

6.2. Drug Accountability

Under Title 21 of the Code of Federal Regulations (21CFR §312.62) the investigator will maintain adequate records of the disposition of the investigational agent, including the date and quantity of the drug received, to whom the drug was dispensed (participant-by-participant accounting), and a detailed accounting of any drug accidentally or deliberately destroyed.

Records for receipt, storage, use, and disposition will be maintained by the study site. A drug-dispensing log will be kept current for each participant. This log will contain the identification of each participant and the date and quantity of drug dispensed.

All records regarding the disposition of the investigational product will be available for inspection by NIAID.

Unused study drugs will be returned to the IDS pharmacy. Unused study drugs will only be re-used if they were never in the hands of the subject. Once the subject has received the drugs, any unused drugs will be destroyed on site.

6.3. Assessment of Participant Compliance with Investigational Agent

Subjects will be asked to bring back any remaining doses of montelukast at Visits 1 and 2, and ifetroban or placebo, at Visit 2. We will provide subjects with bottles for each medication. The number of pills in the bottles will be clearly labeled on the bottle at the time of dispensation. We will also provide subjects with medication diary cards to fill out at home where they will write the number of study medication (ifetroban/placebo) and montelukast pills taken daily.

6.4. Toxicity Prevention and Management

No modifications are permitted.

6.5. Premature Discontinuation of Investigational Agent

Study therapy may be prematurely discontinued for any participant for any of the following reasons:

- A subject has more than one protocol-defined asthma exacerbation (defined as the development of an increase in symptoms of cough, chest tightness, or wheezing [independently of the symptoms anticipated to occur as a result of the aspirin challenge] requiring treatment with oral glucocorticoids. For those subjects maintained with a stable oral glucocorticoid dose, the definition will be an increase of ≥ 10 mg or a doubling of dose, whichever is less)
- The subject experiences gastrointestinal bleeding
- The subject becomes pregnant

Study therapy may also be prematurely discontinued for any participant if the investigator believes that the study treatment is no longer in the best interest of the participant. Subjects that must discontinue the investigational agent will come in for a final visit with a study physician.

7. Other Medications

7.1. Concomitant Medications

7.1.1. Protocol-mandated

Montelukast: Montelukast protects the lower airways from severe reactions in patients undergoing aspirin desensitization and thus increases the safety of aspirin challenges and desensitizations. It is the standard of care to use montelukast as a pre-treatment for patients with AERD undergoing a planned aspirin desensitization, and therefore all participants will be prescribed montelukast 10 mg daily for the duration of the study.

7.1.2. Other permitted concomitant medications

- **Inhaled, oral or nasal corticosteroids:** Participants may enter the trial on such medications based on the underlying condition. No modifications will be made with the exception of a temporary increase in the dose of oral corticosteroids if worsening asthma requires such an intervention. For those patients who require daily oral steroids for their standard maintenance regimen, they must be on no more than a daily dose of 10mg prednisone or equivalent for their standard daily therapy to be considered for inclusion.
- **Inhaled long acting beta-adrenergic agonists and inhaled ipratropium:** participants may enter the trial on such medications based on the underlying condition. No modifications will be made in the course of the trial.
- **Inhaled short acting beta-adrenergic agonists (PRN use):** participants may enter the trial on such medications based on the underlying condition. No modifications will be made in the course of the trial.

7.2. Prophylactic Medications

N/A

7.3. Prohibited Medications

- **Zileuton.** Subjects who were previously taking zileuton will discontinue it at the Screening Visit so as not to interfere with cysLT production and the accurate assessment of clinical symptoms occurring during the aspirin desensitization. A telephone encounter (**Phone Call 1**) 1 week after the Screening Visit will ensure safety and confirm stable asthma for those patients who were asked to discontinue zileuton. Zileuton may be used as a rescue medication during the aspirin desensitization procedure, but the subject must be free of zileuton for at least 3 weeks preceding each Study Visit.
- **Anticoagulants.** Use of warfarin or any other antiplatelet or anticoagulant medications will be prohibited.
- **Beta-blockers.** Due to the risk of bronchospasm associated with beta blockers, current use of any oral beta blocker will be prohibited.
- **NSAIDs.** The use of any additional non-steroidal anti-inflammatory drugs (NSAIDs), except the aspirin dosing as detailed for the study, will be prohibited throughout their participation in the study.
- **Biologics.** The use of any biologics is prohibited in the 120 days prior to Visit 1, and throughout the study.

7.4. Rescue Medications

The following medications can be used during the aspirin desensitization at Visit 2, for patient safety and/or comfort. Only albuterol and ipratropium may be used during the designated 3-hour period of observation following the onset of reaction symptoms. The remaining medications may only be provided for patient comfort after the 3-hour period of observation has concluded.

- **Albuterol.** 90 mcg/puff of MDI albuterol (up to 8 puffs per administration), a total of 3 administrations and 2.5mg of nebulized albuterol may be used as rescue inhalation treatment during the aspirin challenge/desensitization procedures, if bronchospasm occurs.
- **Ipratropium.** 0.5 mg/vial of ipratropium may be used during the aspirin challenge/desensitization procedures, if needed for patient comfort, to relieve any ongoing symptoms of reaction to aspirin if albuterol does not suffice.
- **Zileuton (Zyflo CR).** 1200 mg PO x1-2 may be given for patient comfort due to upper or lower respiratory symptoms, swelling, skin changes, or gastrointestinal discomfort.

- **Prednisone.** 20-50mg PO x1 may be given for patient comfort due to upper or lower respiratory symptoms, swelling, skin changes, or gastrointestinal discomfort.
- **Ondansetron.** 4-8 mg ODT tablet x1 may be given PO for patient comfort due to nausea, vomiting, or gastrointestinal discomfort.
- **Diphenhydramine.** 25 mg PO x1 may be given for patient comfort due to skin changes, itching, congestion, or rhinorrhea.

8. Study Procedures

8.1. Enrollment

Our study population will consist of individuals with suspected AERD referred to the Brigham and Women's Hospital (BWH) Drug Desensitization Program for diagnostic evaluation and potential aspirin challenge/desensitization.

Patients seen in evaluation for suspected AERD in either the Allergy or Pulmonary Clinics at BWH will be identified by their allergist or pulmonologist, and if interest is expressed in aspirin challenge/desensitization and participation in the study, will be offered the opportunity to take home the Consent Form and call back if they wish to participate.

As several of the investigators conducting this study are recognized as specialists in the field of aspirin challenge/desensitization and management of patients with AERD, it is likely that a high proportion of patients with AERD will be identified from within their own clinical practice and referral base at BWH. In order to minimize the possibility that these patients will feel obligated to participate because it is their own physician who is asking, those investigators will initially present the study and offer a Consent Form to take home, and then ask a physician colleague or study coordinator to re-contact the potential study participant.

The research study will be explained in lay terms to each potential research participant. The potential participant will sign an informed consent form before undergoing any study procedures. Once the participant consents to the study and signs the informed consent, the participant is considered enrolled in the study and will be assigned a unique participant number.

8.2. Screening/Baseline Visit

Screening Visit The purpose of the screening visit is to confirm eligibility to continue in the study.

The following procedures, assessments, and laboratory measures will be conducted to determine participant eligibility:

1. A physical exam
2. Spirometry to assess lung function
3. Lab work (urine pregnancy, liver enzymes (AST and ALT), and creatinine level)
4. Assessment of asthma control (ACQ score, which evaluates asthma control over the proceeding 1 week)
5. Assessment of nasal symptoms (SNOT-22 score, which assesses nasal symptoms over the proceeding 2 weeks)
6. Baseline ECG

The labwork is typically completed within 24 hours of the blood draw. After the Screening Visit there is a 2-week Run-in Period in which subjects will begin taking montelukast 10mg daily (if not already on montelukast as part of their regular asthma care). A telephone encounter (Phone Call 1) 1 week later will ensure safety and confirm stable asthma.

8.3. Study Visits

Visit 1 After the 2-week Run-In period on montelukast, subjects will come into the ARC for their baseline visit (Visit 1). The following procedures, assessments, and laboratory measures will be conducted:

1. Interval history, physical exam, ACQ, SNOT-22, TNSS and spirometry will be recorded, along with FeNO.
2. Blood will be drawn for CBC/differential, and the cellular profiling and activation assays.
3. A urine sample will be collected for pregnancy and eicosanoid metabolites. Nasal lavage for cytokine and eicosanoid measurements and a nasal epithelial scraping sample for RNA extraction will be taken.
4. Subjects will be randomized to receive ifetroban (200 mg dose per day), or placebo for 4 weeks.

Subjects will take ifetroban or placebo daily for 4 weeks and will continue taking daily montelukast. There will be a telephone encounter (**Phone Call 2**) 1 week into this Treatment Period to ensure safety and confirm that chronic asthma symptoms have not worsened (as assessed by an ACQ-6 score).

Pharmacokinetic studies of ifebtroban have demonstrated that ifetroban absorption is lower, and maximum plasma concentration is lower, if the drug is taken following a meal. To ensure that absorption of the oral ifetroban is consistent, it is recommended that it should be taken 30 minutes or more prior to a meal. Therefore, we will request that patients take their daily ifetroban or placebo tablets first thing in the morning, at least 30 minutes before their breakfast.

Until institutional guidelines change, all subjects must obtain a negative COVID-19 test result within 72 hours prior to Visit 2. This is to ensure the safety of study staff during the pandemic due to aerosol-generating procedures that may occur at Visit 2. If the COVID-19 test comes back positive, the subject will be informed of their positive results and will be withdrawn from the study. They will receive a safety phone call one week later as follow-up.

Study staff will refer subjects to the current best PCR COVID test available advised by Infectious Disease.

Visit 2 After the 4-week treatment period, subjects will come into the ARC for **Visit 2**.

1. Interval history, physical exam, ACQ, SNOT-22, TNSS and spirometry will be recorded, along with FeNO.
2. Before aspirin is given, a urine sample will be collected for pregnancy and eicosanoid metabolites, and a nasal fluid and nasal epithelial scraping sample will be taken, along with a blood draw for CBC/differential and cellular assays.
3. Subjects will then undergo an oral aspirin desensitization procedure. They will receive an initial 40.5 mg dose of aspirin, and then every 90 minutes will be given increasing doses of 81, 162, and 325 mg aspirin.
4. Vital signs are obtained every 90 minutes during the aspirin challenge/desensitization.
5. If at any point the subject develops symptoms of a reaction, we will examine them and record the time of onset of reaction. The dose of reaction that induces an increase in TNSS of 2 or more points will be recorded as the provocative dose.
6. Following the onset of reaction, patients will be observed for a 3-hour period, during which time no more aspirin doses will be given. TNSS will be recorded at the onset of reaction and again every 30 minutes during this 3-hour period after reaction.
7. Pulmonary function testing is repeated before each dose and at the onset of reaction and if it remains within 85% of their pre-challenge FEV₁, it will be repeated every 90 minutes during the 3-hour period after reaction. If the FEV₁ falls by 15% or more from their morning pre-challenge FEV₁, they will be treated with

MDI albuterol (up to 8 puffs per administration), followed by nebulized albuterol if needed and FEV₁ will be repeated every 30 minutes until it has returned to within 85% of their morning pre-challenge FEV₁.

8. No medications (except albuterol and ipratropium) will be used for relief of symptoms during the desensitization until the 3-hour period of observation following onset of reaction is completed, unless required for a patient's safety.
9. A blood sample will be collected 1 hour after the onset of reaction for CBC/differential, platelet activation assays, and platelet-leukocyte aggregate measurements. Urine and nasal fluid samples will be collected 90 minutes after the onset of reaction, or if there is no clinical reaction at all, will be collected 90 minutes after the 325mg dose of aspirin is given.

Upon completion of the 3-hour period of observation, the subject will receive the provocative dose for a second time followed by the next subsequent aspirin dose after 90 minute observation intervals. Once the subject has effectively tolerated, as determined by a study physician, the repeat provocative dose and one subsequent dose bringing the cumulative dose of aspirin ingested during the procedure to ≥ 325 mg, the subject will be discharged home 90 minutes after the last dose, and will be instructed to begin taking daily aspirin, 325mg twice daily for a week until the Phone Call 3, as is part of our standard-of-care for these patients.

Following the 3-hour period of observation, the rescue medications described in Section 7.4 may be used for patient comfort. A sufficient 2-week supply of aspirin will be provided for patients so that they have enough to have them continue daily aspirin through the 2-week follow-up phase.

Follow-up Phase (2 weeks): During the follow-up phase, safety will be assessed through a telephone interview (Phone Call 3) 1 week after **Visit 2** to recommend the patient increases their daily aspirin dose from 325mg twice daily to 650mg twice daily, and again through a telephone interview (Phone Call 4) 1 week after that dose increase to ensure that the patient is tolerating the 650mg twice daily aspirin therapy and to ensure that the patient has an appropriate follow-up visit scheduled with their primary provider within 2 months of initiating the daily aspirin therapy. In order to ensure patient safety and consistency, patients will be prescribed sufficient montelukast at the Screening Visit to have them continue daily montelukast through this follow-up phase.

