Secondary Endpoint(s)	
1. Severity of bronchoconstriction (as measured by maximum fall in FEV₁ during the aspirin-induced reaction) during the aspirin-induced reaction at Visit 2, compared between patients on placebo vs ifetroban, with the changes also analyzed with provocative aspirin dose as a covariate.
 
2. Increase of urinary, and nasal lavage levels of LTE₄ during aspirin-induced reaction from Visit 2 pre-aspirin levels, compared between patients on placebo vs ifetroban, with the changes also analyzed with provocative aspirin dose as a covariate.
 
3. Change from Visit 1 in baseline FEV₁, Asthma Control Questionnaire (ACQ), and Sino-Nasal Outcome Test (SNOT-22) at Visit 2, compared between patients on placebo vs ifetroban.
 
4. Change in levels of other urinary, and nasal eicosanoids, and levels of plasma/serum and nasal tryptase, from Visit 1 to Visit 2 pre-aspirin challenge and Visit 2 pre-aspirin to during the aspirin-induced reaction at Visit 2, compared between patients on placebo vs ifetroban, with the changes also analyzed with provocative aspirin dose as a covariate.
 
5. Change from Visit 1 in baseline exhaled nitric oxide (FeNO) levels at Visit 2, compared between patients on placebo vs ifetroban.

	6. Change in numbers/percentages of activated platelets and platelet-leukocyte aggregates in the peripheral blood from Visit 1 to Visit 2 baseline (pre-aspirin administration) and during the aspirin-induced reaction at Visit 2 from Visit 2 baseline, compared between patients on placebo vs ifetroban, with the changes also analyzed with provocative aspirin dose as a covariate.
Accrual Objective	50 subjects
Study Duration	36 months
Treatment Description	Ifetroban and aspirin
Inclusion Criteria	
 1. History of AERD, defined as meeting the diagnostic triad with: 
 1. History of physician-diagnosed asthma and 2. History of physician-diagnosed nasal polyposis and 3. History of pathognomonic reactions aspirin or other nonselective COX inhibitors. 2. Stable asthma (post-bronchodilator FEV₁ of ≥70%, no glucocorticoid burst for at least 2 weeks prior to Visit 1, and no hospitalizations or ER visits for asthma for at least the prior 6 months) 3. Age between 18 and 70 years 4. No current smoking (not more than one instance of smoking in the last 3 months) 5. Non-pregnant

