Following the onset of reaction, patients will be observed for a 3-hour period, during which time no more aspirin doses will be given. TNSS will be recorded at the onset of reaction and again every 30 minutes during this 3-hour period after reaction. Pulmonary function testing is repeated before each dose and at the onset of reaction and if it remains within 85% of their pre-challenge FEV₁, it will be repeated every 90 minutes during the 3-hour period after reaction. If the FEV₁ falls by 15% or more from their morning FEV₁, they will be treated with albuterol, administered by metered dose inhaler (MDI), (up to 8 puffs per administration), and FEV₁ will be repeated every 30 minutes until it has returned to within 85% of their morning pre-challenge FEV₁. If after 3 rounds of albuterol administered by MDI (a total of 24 puffs), the subject's FEV₁ has not returned to within 85% of their morning pre-challenge FEV₁, nebulized albuterol will be administered. No medications (except albuterol and ipratropium) will be used for relief of symptoms during the desensitization until the 3-hour period of observation following onset of reaction is completed, unless required for a patient's safety. A blood sample will be collected 1 hour after the onset of reaction for CBC/differential, platelet activation assays, and platelet-leukocyte aggregate measurements. Urine and nasal samples will be collected at the onset of reaction, and again 90 minutes and 3 hours after the onset of reaction, or if there is no clinical reaction at all, will be collected 90 minutes after the 325mg dose of aspirin is given.

Upon completion of the 3-hour period of observation, further aspirin doses will be administered every 90 minutes until a state of clinical desensitization to and tolerance of 325 mg of aspirin is achieved. Patients will be discharged home 90 minutes after ingestion of 325 mg of aspirin and will be instructed to begin taking daily aspirin, as is part of our standard-of-care for these patients. If required due to time constraints, this visit could proceed onto the next day, during which the subject would begin by repeating the aspirin dose they ended with the day before. However, 95% of our aspirin desensitization procedures done as part of clinical patient care are completed within the first day.

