13.4.4 Analyses of Secondary and Other Endpoint(s)/Outcome(s)

Using a two-sided two-sample t-test for mean difference with unequal variance we will compare each secondary outcome (aspirin-induced fall in FEV_1 , aspirin-induced peak urinary LTE_4 and serum/nasal tryptase) separately on treatment with ifetroban or placebo. Based on our current internal clinical data:

- i. We estimate an average maximum aspirin-induced fall in FEV₁ of 14.6% with a standard deviation of 8.3. With 20 patients per treatment group, we will have 72% power to detect a 50% difference in the fall of FEV₁ at a 0.05 level of significance.
- ii. We estimate an average aspirin-induced peak urinary LTE₄ of 6.0 ng/mg Cr with a standard deviation of 3.9. With 20 patients per treatment group, we will have 74% power to detect a difference of 2.4 ng/mg Cr (or a 40% decrease in the rise in LTE₄) at a 0.05 level of significance.

We will compare each outcome (ifetroban-induced changes in baseline FEV₁, asthma control (ACQ), nasal symptoms (SNOT-22), FeNO and baseline LTE₄) separately after 4 weeks of treatment with ifetroban or placebo using a two-sided two-sample t-test. Based on our current internal clinical baseline data of 25 patients with AERD:

- iii. We estimate an average baseline FEV₁ of 92% predicted and a standard deviation of 9.8, we will have 78% power to detect a difference in FEV₁ of 6%, at a 0.05 level of significance.
- iv. We estimate an average baseline ACQ of 0.64 and a standard deviation of 0.54, we will have 82% power to detect a difference of 0.35 points, at a 0.05 level of significance. A fall in ACQ of 0.5 points is consistent with clinically significant improvement.³³
- v. We estimate an average baseline SNOT-22 score of 38 and a standard deviation of 14, we will have 86% power to detect a difference of 9 points, at a 0.05 level of significance. A fall in SNOT-22 score of 8.9 is consistent with clinically significant improvement.³⁴

We estimate an average baseline urinary LTE₄ of 0.37 ng/mg Cr and a standard deviation of 0.22, we will have 80% power to detect a difference of 0.14 ng/mg Cr (or a decrease in urinary LTE₄ of 30% from baseline, roughly half of the effect of zileuton,^{35,36} at a 0.05 level of significance.

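### Sections 3.1 and 8.3 disagree on when reaction urine is collected at Visit 2, and neither controls voiding, so the LTE4 rise can be diluted by pre-reaction urine to an unknown and possibly arm-dependent extent

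*Combined protocol and SAP*

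**What the plan says.** **Section 8.3 (Visit 2, items 2 and 9).** The pre-aspirin collection is "Before aspirin is given, a urine sample will be collected for pregnancy and eicosanoid metabolites". The only later urine listed for a reactor is "Urine and nasal fluid samples will be collected 90 minutes after the onset of reaction". For subjects who never react, the sample "if there is no clinical reaction at all, will be collected 90 minutes after the 325mg dose of aspirin is given".

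**Section 3.1.** For the same visit: "Urine and nasal samples will be collected at the onset of reaction, and again 90 minutes and 3 hours after the onset of reaction". Its non-reactor rule is the same as in 8.3.

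**Schedule of Events (Appendix 1).** Urine eicosanoids at Visit 2 carry only a double plus sign, which does not settle the matter.

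**Timing.** "They will receive an initial 40.5 mg dose of aspirin, and then every 90 minutes will be given increasing doses", so the four doses fall at 0, 90, 180 and 270 minutes.

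**Endpoint and test.** The synopsis defines the secondary endpoint as "Increase of urinary, and nasal lavage levels of LTE₄ during aspirin-induced reaction from Visit 2 pre-aspirin levels". Section 3.3 calls the cysLT comparison a proof of mechanism. Section 13.4.4 specifies an unadjusted two-sided Welch t-test on peak urinary LTE4, expressed per mg creatinine. The synopsis and 3.3 add an analysis with provocative dose as a covariate, coded 1 to 4.

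No section requires a complete void, restricts voiding between samples, or records void times.

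**The concern.** A urine sample holds everything excreted since the bladder was last emptied. Under 8.3 the last scheduled void before the reaction sample is the pre-aspirin one. Anything formed during the dose steps and not passed in between is therefore mixed with the 90 minutes of reaction urine. Dividing by creatinine corrects for water intake. It does not correct for this mixing, because pre-reaction urine brings its own creatinine with LTE4 at baseline level.

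There are two consequences. First, the measured rise is attenuated by an amount that varies between subjects, which costs precision in an endpoint with 20 per arm. Second, a later reaction allows more pre-reaction urine to accumulate. Section 13.4.2 expects ifetroban to move mean PD2 from 60 to 180, so dilution could differ by arm and delay could be mistaken for reduced cysLT synthesis. The onset sample in 3.1 would prevent this for reactors if it were a complete void. The protocol does not say so, and 8.3 omits the sample. For non-reactors, neither section schedules a void over the 270 + 90 = 360 minutes from first dose to sample.

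**Working it through.** **The plan's own figure.** Section 13.4.4 says "we will have 74% power to detect a difference of 2.4 ng/mg Cr", with mean 6.0, SD 3.9 and 20 per arm; 2.4/6.0 = 40%. A two-sided two-sample t-test with these inputs gives 47.5%. A paired or one-sample t-test with n = 20 gives 74.2%. So 74% does not reproduce with the stated test. That is a separate matter, and nothing below depends on it.

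**Inputs from the documents.** Dose times 0, 90, 180 and 270 min (8.3); reaction LTE4 6.0 (SD 3.9) and baseline 0.37 (SD 0.22) ng/mg Cr, 20 per arm, Welch test (13.4.4).

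**Assumptions not in the documents.** Creatinine excretion is constant. LTE4 generation is the same in both arms and at every dose. Onset is 60 min after the provoking dose (30-90 min in simulation). Provoking-dose shares for 40.5/81/162/325 mg are 30/45/20/5% on placebo, and 10/30/35/25% (A) or 5/20/35/40% (B) on ifetroban.

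**Formula.** Reaction share of the sample = 90 / (90 + minutes of pre-onset urine still in the bladder). The measured rise is proportional to this share.

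**No void between samples.**

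| Provoking dose (mg) | Minutes to onset | Share |
|---|---|---|
| 40.5 | 60 | 90/150 = 0.600 |
| 81 | 150 | 90/240 = 0.375 |
| 162 | 240 | 90/330 = 0.273 |
| 325 | 330 | 90/420 = 0.214 |

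- 81 to 162 mg: 0.273/0.375 = 0.73, a 27% lower rise. 81 to 325 mg: 0.214/0.375 = 0.57, 43% lower.
- Placebo mean share: 0.30×0.600 + 0.45×0.375 + 0.20×0.273 + 0.05×0.214 = 0.414.
- Ifetroban A: 0.10×0.600 + 0.30×0.375 + 0.35×0.273 + 0.25×0.214 = 0.322. Ratio 0.322/0.414 = 0.78, a spurious 22% fall.
- Ifetroban B: 0.05×0.600 + 0.20×0.375 + 0.35×0.273 + 0.40×0.214 = 0.286. Ratio 0.286/0.414 = 0.69, a 31% fall.

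**Simulation with no true LTE4 effect** (lognormal, CV 3.9/6.0 = 0.65; 20 per arm; Welch test):

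| Voiding before the 90-minute sample | Spurious fall on ifetroban | Rejection at 0.05 |
|---|---|---|
| Complete void at onset | 0 | about 4-5% |
| None | 22-31% | 16-29% |
| One, at a random time before onset | 14-19% | 8-13% |
| Regular, intervals within 1.5-4 h | about 0 | 4-5% |
| Longer intervals | sign can reverse | not fixed |

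The reversal can be seen by hand. Suppose everyone voids 270 min after the pre-aspirin sample. A reaction at 81 mg (onset 150, sample 240 min) has had no void, so its share is 0.375. A reaction at 325 mg (onset 330) holds only 330 − 270 = 60 min of earlier urine, so its share is 90/150 = 0.600. The later reaction is now the less diluted one.

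**Attenuation and variance.** Across the voiding patterns without an onset void, the rise is about 8-58% lower and its CV rises from 0.70 to 0.71-0.86. The upper end of the attenuation is the no-void case in the placebo mix (1 − 0.414 = 59% by the sum above).

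**The case against.** The strongest objection is that Section 3.1 already schedules an onset sample. If it governs and subjects empty their bladders, reactors have no problem. That stands, so for reactors the defect is a contradiction plus an unstated complete void. It is not a settled design without an onset sample.

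Second, nobody is asked to hold urine for hours, and Section 6.1.3.2 has aspirin taken with plenty of water. With ordinary regular voiding the difference between arms is about zero. This also stands. What survives is the attenuation and added variance, and the fact that unrecorded voids cannot be corrected afterwards.

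Third, the planned dose covariate tracks elapsed time at 90 minutes per step. In the no-void simulation the dose-adjusted test rejects about 4-5% of the time. It is a real safeguard, but a partial one: it is an additional analysis, the powered test is unadjusted, and provoking dose is a post-randomisation variable that treatment may change.

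A reader might infer that the plan will make ifetroban look like a suppressor of LTE4, or that type I error is inflated outright. The documents do not support either. If ifetroban does nothing, provoking doses match between arms and no bias arises. The bias needs a drug that delays reactions without changing LTE4, together with infrequent voiding. Later reactors have also taken more aspirin, which may itself change LTE4, so the net direction is open.

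**Conclusion.** The point holds as a contradiction between 3.1 and 8.3 with a measurable cost. Following 8.3 as written lets pre-reaction urine into the sample behind the proof-of-mechanism endpoint, lowers the measured rise and adds variance. A between-arm bias is possible, from a spurious 31% fall through zero to the opposite sign, but its size and direction cannot be fixed from the documents. The figures rest on assumed dose shares, onset times, voiding patterns and constant creatinine excretion. They also take 6.0 ng/mg Cr as the undiluted reaction level, which the protocol does not confirm. The non-reactor gap remains even if 3.1 governs. A low-cost change is justified, but a claim that the LTE4 comparison is biased in ifetroban's favour is not.

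**What to change.** 1. Reconcile the two sections by carrying the onset urine sample from 3.1 into 8.3 item 9, and state whether the 3-hour sample is kept and whether it contributes to peak LTE4.
2. Make the onset sample a complete void.
3. Record the time of every void from the pre-aspirin sample onward.
4. Define the reaction LTE4 value as urine formed between the onset void and the 90-minute sample.
5. For non-reactors, in both sections, add a void just before the 325 mg dose and use urine formed from then to the sample 90 minutes later.

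Routine voids before every dose are not needed. The cost is one or two scheduled voids and a CRF time field, with no added visit. An onset void may be missed during a reaction; the recorded times then support a sensitivity analysis that scales the rise by the collection interval, (minutes since last void)/90.
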